#### 7.2.1.2 Subject analysis sets

The main analysis populations are defined below. In the TSAP, further analysis data sets may be defined. Patients will be analysed according to the assigned treatment, unless otherwise specified. Patients who are replaced during the DLE evaluation period will be excluded from the determination of the MTD (see [Section 3.1](#)).

Important protocol deviations (iPDs) will be defined in the Integrated Quality and Risk Management (IQRM) plan. IPDs will be identified no later than in the Report Planning Meeting, and the iPD categories will be updated as needed. The handling of patients with iPDs will be described in the TSAP.

#### Treated Set (TS)

The TS will consist of all patients who were treated with at least one dose of BI 754132.

#### Pharmacokinetic parameter analysis set (PKS)

This set includes all subjects in the TS who provide at least one plasma sample for determination of PK parameters that was not excluded due to a protocol violation relevant to the evaluation of PK or due to PK non-evaluability (as specified below).

The pharmacokinetic parameters listed in [Sections 2.1.3](#) and [2.2.2](#) for BI 754132 will be determined according to the relevant SOP of the Sponsor (001-MCS-36-472).

Plasma concentration data and parameters of a subject will be included in the PK analyses if they are not flagged for exclusion due to a protocol violation relevant to the evaluation of PK (to be decided no later than in the Report Planning Meeting) or due to PK non-evaluability (as revealed during data analysis, based on the criteria specified below). Exclusion of a subject's data will be documented in the CTR.

Relevant protocol violations may be

- Incorrect trial medication taken, i.e. the subject received at least one dose of trial medication the subject was not assigned to
- Incorrect dose of trial medication taken
- Use of restricted medications

Plasma concentrations and/or parameters of a subject will be considered as non-evaluable, if for example, there were missing samples/concentration data at important phases of PK disposition curve.

Plasma concentration data and parameters of a subject which is flagged for exclusion will be reported with its individual values but will not be included in the statistical analyses.

Only concentration values within the validated concentration range and actual sampling times will be used for the calculation of pharmacokinetic parameters. Concentrations used in the pharmacokinetic calculations will be in the same format as in the bioanalytical report (that is to the same number of decimal places provided in the bioanalytical report).

### 7.2.2 Primary endpoint analyses

#### SRD part:

The primary safety endpoint “Number of patients with ocular (in the study eye) and systemic DLEs from drug administration till EOT” will be analysed descriptively, based on the TS.

For the definition of DLEs, please refer to [Section 5.2.1](#).

#### MD part:

The primary safety endpoint “Number of patients with drug-related AEs from drug administration until EOT” will be analysed descriptively, based on the TS.

### 7.2.3 Secondary endpoint analyses

All secondary safety endpoints defined in [Section 2.1.3](#) will be analysed descriptively, based on the TS.

#### SRD part:

The PK endpoints  $C_{max}$ ,  $AUC_{0-\infty}$ , and  $t_{max}$  specified in [Section 2.1.3](#) will be analysed descriptively, based on the PKS. Dose proportionality will be explored descriptively for the PK endpoints  $AUC_{0-\infty}$  and  $C_{max}$  if feasible.

#### MD part:

Systemic exposure of BI 754132 after multiple IVT doses by determination of  $C_{min,1}$  and  $C_{min,2}$  (trough levels before second and third administrations) and plasma concentrations 4, 8 and 14 weeks after the third administration will be determined in the MD part along with descriptive statistics, based on the PKS.

### 7.2.5 Safety analyses

Adverse events will be coded using the Medical Dictionary for Drug Regulatory Activities (MedDRA). Standard BI summary tables and listings will be produced. For BI 754132, the residual effect period (REP) after IVT administration is not known. Therefore, all AEs with

an onset between start of treatment and the respective EOT visit will be assigned to the on-treatment period for evaluation. The safety analysis will be performed by planned dose group.

All treated patients will be included in the safety analysis. In general, safety analyses will be descriptive in nature and will be based on BI standards. No hypothesis testing is planned.

Statistical analysis and reporting of adverse events will concentrate on treatment-emergent adverse events, i.e. all adverse events occurring between start of treatment and the EOT visit. Adverse events that start before first drug intake and deteriorate under treatment will also be considered as ‘treatment-emergent’.

Frequency, severity, and causal relationship of adverse events will be tabulated by system organ class and preferred term after coding according to the current version of the Medical Dictionary for Drug Regulatory Activities (MedDRA) at database lock.

Laboratory data will be analysed both quantitatively as well as qualitatively. The latter will be done via comparison of laboratory data to their reference ranges. Values outside the reference range as well as values defined as clinically relevant will be summarised. Treatment groups will be compared descriptively with regard to distribution parameters as well as with regard to frequency and percentage of patients with abnormal values or clinically relevant abnormal values.

Vital signs, physical examinations, or other safety-relevant data observed at screening, baseline, during the course of the trial and at the end-of-trial evaluation will be assessed with regard to possible changes compared to findings before start of treatment.

A centralised evaluation of all 12-lead ECGs recordings (see [Section 5.2.6](#)) will be the basis for the ECG variables QT, HR, QTcF, PR, QRS, RR, and further derived ECG endpoints. The baseline value of an ECG variable is defined as the mean of the ECG measurements prior to drug administration. The derivation of the quantitative and qualitative ECG endpoints and their analyses will be described in the TSAP.

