#### **4. CHANGES IN THE PLANNED ANALYSIS OF THE STUDY**

All analyses as planned in the CTP will be performed and are described in more detail in this TSAP. The following changes compared to the protocol will be made:

- The additional analysis set 'Enrolled set' was defined, which is used for disposition tables and listings, see [Section 6.3](#).
- The additional analysis set 'Entered set' was defined, which is used in disposition tables and listings, see Section 6.3.
- The additional analysis set 'DLE evaluable set' was defined for the SRD part, which is used for SMC outputs related to the BLRM, see Section 6.3.

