#### **CTP Section 7.2.5:**

*For BI 754132, the residual effect period (REP) after IVT administration is not known. Therefore, all AEs with an onset between start of treatment and the respective EOT visit will be assigned to the on treatment period for evaluation.*

The following separate study phases will be defined for the analyses of AEs:

- **Screening** (ranging from 0:00h (midnight) on day of informed consent until first administration time of BI 754132)
- **On treatment**
  - **BI treatment** (separately for each treatment, ranging from the time of first administration of BI 754132 until 0:00h (midnight) on the day after trial completion date)

Please note that all AEs reported between start of trial drug administration and the last per-protocol contact will be considered on treatment (i.e. no follow-up period is considered in this trial).

The following AE displays will be provided in the report:

Section 15.3 and Appendix 16.1.13.1.8 (for ClinicalTrials.gov and EudraCT) of the CTR displays:

In these displays, the on treatment phase will be analysed (labelled with the short label of the study treatment). Screening will not be included in this analysis.

The following totals will be provided in addition in Section 15.3:

- a total over all on treatment phases included in this analysis ("Total") (SRD part only)

In Section 15.4 and Appendix 16.2 (Listings) of the CTR displays, the screening period will be included and no totals will be provided.

For detailed information on the handling of the treatments refer to Technical TSAP ADS (analysis data set) plan and Analysis Data Reviewers guide.

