## 7.3 TREATMENT COMPLIANCE

**Section 4.3 of the CTP:** *Compliance will be assured by administration of all trial medication in the study centre under supervision of the investigating physician or a designee. The measured sample concentrations will provide additional confirmation of compliance.*

It is not intended to list the compliance separately. Any deviations from complete intake will be addressed in the RPM/DBLM (see [Section 6.2](#)) and described in the CTR.

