## **7.8 SAFETY ANALYSIS**

All safety analyses will be performed on the TS.

If not stated otherwise, the safety results will be sorted by treatment group.

The safety data for treated patients who failed to complete the study (dropouts or withdrawals) will be reported as far as their data are available. All withdrawals will be documented and the reason for withdrawal recorded.

Per the European Union (EU) Regulation 536/2014 (Annex V, Point 4) ([17](#)), the following information will be included in Appendix 16.1.13.1 of CTR:

- number of patients included by country
- number of patients inside (member states) and outside the EU (third countries)
- frequency of serious drug-related AEs by treatment, primary system organ class and preferred term.

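### Safety is grouped by planned dose, so a misdosed patient's adverse events would be tabulated under a dose that patient did not receive

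*Protocol*

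**What the plan says.** - **Grouping rule.** Protocol Section 7.2.5: "The safety analysis will be performed by planned dose group". The general default in Section 7.2.1.2 agrees: "Patients will be analysed according to the assigned treatment, unless otherwise specified". Nothing is specified otherwise for safety.
- **Population.** Protocol Section 7.2.5: "All treated patients will be included in the safety analysis". A misdosed patient therefore stays in the tables.
- **SAP.** Section 4 says "All analyses as planned in the CTP will be performed and are described in more detail in this TSAP", and its three listed changes only add analysis sets. Section 7.8 says "If not stated otherwise, the safety results will be sorted by treatment group", without saying whether that means planned or received dose. Section 6.1 defers further: "For detailed information on the handling of the treatments refer to Technical TSAP ADS (analysis data set) plan and Analysis Data Reviewers guide". Those two documents are not available to us.
- **Misdosing.** For pharmacokinetics (PK), Protocol Section 7.2.1.2 gives "Incorrect dose of trial medication taken" as an example of what a relevant protocol violation may be. There is no counterpart for safety. SAP Section 7.3 says "Any deviations from complete intake will be addressed in the RPM/DBLM" and that such deviations are described in the trial report.

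**The concern.** Analysis as assigned exists to protect a randomised comparison. Here there is no randomisation, blinding, control group or hypothesis test (Protocol Sections 3.1 and 7.1). The trial is meant to establish a safe and tolerable dose (Section 3.2), and that is a question about the dose received.

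A discrepancy is possible. A site pharmacist prepares each injection from a 60 mg vial and diluent (Sections 4.1.1 and 4.1.4), and the SRD doses span a twentyfold range (6 / 0.3 = 20). The PK text shows that the sponsor has thought of incorrect doses. As written, the same patient could be left out of the PK summaries because of the dose received and still be counted for safety under the dose planned.

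At stake is the attribution of adverse events to doses in groups of three to six patients.

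**Working it through.** **1. Group sizes.** The synopsis plans 3 patients per dose and 6 at the final dose: 3 + 3 + 3 + 6 = 15, the figure in Protocol Section 7.5. Adding 3 if DLEs occur gives 18, and adding 6 MD patients gives 24, both as stated. Section 1.2 reports that 3, 3, 3 and 6 patients completed the SRD part.

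**2. Effect on a tabulated rate.** Rate = r/n. Assume one misdosed patient with one adverse event of a given type, and no such event in the other patients of the 3 mg and 6 mg groups. Exact 95% intervals are in brackets.

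| Case | Grouping | 3 mg | 6 mg |
|---|---|---|---|
| Planned 3 mg, received 6 mg | planned | 1/3 = 33% (1–91%) | 0/6 = 0% (0–46%) |
| | received | 0/2 = 0% (0–84%) | 1/7 = 14% (0–58%) |
| Planned 6 mg, received 3 mg | planned | 0/3 = 0% (0–71%) | 1/6 = 17% (0–64%) |
| | received | 1/4 = 25% (1–81%) | 0/5 = 0% (0–52%) |

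For a group of three, the misattributed event is worth 33 − 0 = 33 points. In the six-patient group it is worth 14 to 17 points. The intervals overlap heavily, so what changes is the displayed pattern across doses; no formal inference changes.

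**3. BLRM, as illustration only.** The documents do not say which dose enters the model. Inputs are from Protocol Section 7.2.1.1: logit(π_d) = log α + β·log(d/6), the three-component prior in Table 7.2.1.1: 1, and the overdose-control (EWOC) criterion P(OD) = P(π_d > 0.25 | data) < 0.25. Integrating over a grid gives these current-dose values of P(OD) against Table 10.4: 1:

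| Scenario | 1 | 2 | 3 | 3b | 4 | 6 | 7 | 8 | 9 |
|---|---|---|---|---|---|---|---|---|---|
| Recomputed | 0.017 | 0.313 | 0.013 | 0.012 | 0.195 | 0.207 | 0.258 | 0.112 | 0.371 |
| Table | 0.015 | 0.309 | 0.012 | 0.013 | 0.202 | 0.218 | 0.253 | 0.113 | 0.364 |

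The largest gap is 0.218 − 0.207 = 0.011, so the model is reproduced closely enough.

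Now suppose one misdosed patient has a DLE during escalation, with no other DLE:

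| Planned → received | Data by planned dose | Data by received dose | P(OD), planned vs received |
|---|---|---|---|
| 3 → 6 mg | 0.3: 0/3, 1: 0/3, 3: 1/3 | 0.3: 0/3, 1: 0/3, 3: 0/2, 6: 1/1 | 3 mg: 0.207 vs 0.145; 6 mg: 0.450 vs 0.501 |
| 1 → 3 mg | 0.3: 0/3, 1: 1/3 | 0.3: 0/3, 1: 0/2, 3: 1/1 | 1 mg: 0.195 vs 0.130; 3 mg: 0.427 vs 0.411 |
| 6 → 3 mg | 0.3: 0/3, 1: 0/3, 3: 0/3, 6: 1/3 | 0.3: 0/3, 1: 0/3, 3: 1/4, 6: 0/2 | 6 mg: 0.258 vs 0.220 |
| 0.3 → 1 mg | 0.3: 1/3 | 0.3: 0/2, 1: 1/1 | 0.3 mg: 0.313 vs 0.235 |

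The first two cases change no EWOC result at the doses shown: values below 0.25 stay below, and values above stay above. The last two cross the limit. The third is marginal, since 0.258 − 0.250 = 0.008 is smaller than the reproduction gap, although Table 10.4: 1 itself gives 0.253 for the same data.

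**4. What the reported data leave open.** Section 1.2 reports no DLE in the completed SRD part, so no DLE count can move between doses. The data pattern is that of scenario 3b, with P(OD) at 6 mg of 0.013. Regrouping a patient without a DLE would change denominators only. What could still move is the attribution of the reported 12 ocular and 20 systemic adverse events, and only if a misdose occurred. The MD part has one dose group (SAP Table 6.1: 1), so there is no second MD group to misattribute to.

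**The case against.** Four points can be made for the plan.

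- **A misdose would be visible.** Dosing is supervised on site (Protocol 4.3), the Safety Monitoring Committee hears each patient's course (4.1.3), deviations in drug administration are reviewed and important ones summarised and listed (SAP 6.2), and individual values are listed (SAP 7). This stands and limits the harm. But none of these steps regroups the summary tables.
- **The technical analysis-data-set plan may derive actual treatment.** We cannot judge that. If it does, it departs from Protocol 7.2.5, and the departure is missing from the changes listed in SAP Section 4.
- **The scenario is largely closed.** The SRD part is complete, without a DLE or a reported misdose. This stands, and it is why the point is minor.
- **The BLRM is a separate matter.** Section 7.2.1.1 speaks of a dose d without saying planned or received, and says the BLRM is not used for the primary endpoint. This also stands.

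A reader might infer from the examples above that planned-dose grouping could have misdirected escalation. The documents do not support that: the dose entering the model is unspecified, no DLE occurred, and the 3 to 6 mg example leaves EWOC status unchanged at both doses. A reader might also infer that misdosed patients are automatically dropped from PK. The text makes an incorrect dose only a possible reason, decided no later than the Report Planning Meeting.

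**Conclusion.** The point holds as a minor one. The protocol states a planned-dose rule for safety, the SAP text does not override it, and the rule has no benefit in this design. For any patient whose received dose differed from the planned dose, adverse events would be tabulated under the wrong dose. One event is then worth about 33 points in a group of three.

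This rests on a condition that the documents do not show to have occurred: no misdosing is reported in the text available to us. With no SRD DLE and a single MD dose group, the practical reach is the SRD adverse-event tables and the denominators of the DLE table and final BLRM. If every patient received the planned dose, nothing changes.

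**What to change.** - **Protocol 7.2.5 and SAP 7.8:** state that safety and DLEs are summarised by dose actually received and that any discrepancy from the planned dose is listed. Keep planned dose for disposition.
- **Protocol 7.2.1.2:** cross-refer to this as the exception to the assigned-treatment default.
- **SAP 7.4:** state that the final BLRM uses the dose received.
- **SAP 4:** list this as a change if the protocol itself is not amended.

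The cost is a few sentences. Sample size is unaffected (the SRD part stays at 15), no new data need be collected if the dose given is already recorded, and results are identical if no dosing error occurred.

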## **7.2.6      Other Analyses**

Not applicable.

## **7.2.7      Interim Analyses**

The sponsor will continuously monitor the safety. The dose escalation design of the SRD part foresees that the sponsor and the SMC perform regular safety evaluations. These evaluations will be unblinded to dose.

An exploratory PK analysis will be performed after each dose group of the SRD part to check the systemic exposure of BI 754132.

### **7.3 HANDLING OF MISSING DATA**

Missing baseline laboratory values will be imputed by the respective values from the screening visit. No other imputations will be performed on missing data although every effort will be made to obtain complete information on all AEs, with particular emphasis on potential DLEs.

### **7.4 RANDOMISATION**

No randomisation will be performed. Patients will be assigned to escalating dose groups of the SRD part or to the MD part by order of admission into the trial.

### **7.5 DETERMINATION OF SAMPLE SIZE**

#### SRD part:

If no DLE occurs, 15 DLE evaluable patients will be treated in this trial part, based on the planned number of dose levels that are tested and on the requirement to have 6 DLE evaluable patients in the last dose group (see [Section 3.1](#)). However, the actual number of patients will depend on the actual number of dose cohorts tested and on the occurrence of DLEs. Based on the simulation study to evaluate operating characteristics of the BLRM (see [Appendix 10.4](#)), about 17 evaluable patients are expected to be treated in the dose escalation part for the model to have reasonable operating characteristics relating to its MTD recommendation.

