	

• <math>AUC_{0-\infty}</math> (area under the concentration-time curve of BI 754132 in serum over the time interval from 0 extrapolated to infinity)

• <math>t_{max}</math> (time from dosing to maximum serum concentration of BI 754132)

 
MD part:
 

• Systemic exposure of BI 754132 after multiple IVT dosing by determination of <math>C_{min,1}</math> and <math>C_{min,2}</math> (trough levels before second and third administrations) and plasma concentrations 4, 8 and 14 weeks after the third administration

Trial design	This trial will consist of an SRD part followed by an MD part. Both parts will be open label, uncontrolled and non-randomized.
Total number of patients entered	Up to 24 in total; 18 patients (planned 15 plus 3 additional if DLEs occur) in the SRD part and 6 patients in the MD part.
Number of patients on each treatment	Planned: 3 per dose group and 6 at final dose in SRD part (actual numbers depending on the dose escalation decisions taken by the Safety Monitoring Committee (SMC)) and 6 at the dose of the MD part
Diagnosis	Patients with geographic atrophy secondary to age-related macular degeneration
Main in- and exclusion criteria	
Inclusion: Men and women over the age of 50 with GA lesion at least 0.75 disk area in size and a best corrected visual acuity (BCVA) of 20/100 to 20/400 (SRD part) and 20/100 or lower (MD part) Snellen equivalent measured by the Early Treatment Diabetic Retinopathy Study protocol.
 
Exclusion: Additional eye disease that could compromise BCVA.

Test product(s)	BI 754132
dose	SRD part: 4 dose groups, 0.3 mg, 1 mg, 3 mg, 6 mg (single doses) MD part: The highest dose (e.g. 6 mg) established as safe and tolerable dose during the SRD part
mode of administration	Intravitreal
Duration of treatment	SRD part: Single intravitreal dose MD part: 3 intravitreal doses in 4-weekly intervals (q4w)
Statistical methods	Descriptive statistics will be provided for all endpoints. The dose escalation in the SRD part will be guided by a Bayesian logistic regression model (BLRM) with overdose control that will be fitted to binary toxicity outcomes. The estimates of parameters will be updated as data are accumulated using the BLM.

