#### Toxicology

The toxicology data suggest BI 754132 can be safely administered via IVT to humans for up to 13 weeks. Given that the tolerability and immunogenicity profiles in human may be different from those in cynomolgus monkey, the potential inflammatory and immunogenicity responses in human should be closely monitored. Escalation of doses in human should be based on the tolerability in the earlier cohorts and the maximum dose in human should not exceed 6 mg/eye. Potential systemic effects including body weight, heart rate, blood pressure and hematology should be monitored based on the findings in the cynomolgus studies (see [Section 1.4.2](#) and IB [[c22785135](#)] Section 5.3 for further details).

BI 754132 is a human IgG1 carrying FcR-gamma receptor binding mutations for reducing ADCC and CDC. BI 754132, an agonist for the TrkB receptor, binds to the extracellular domain causing auto-phosphorylation and induction of downstream signaling cascades for increased cell survival and synaptogenesis. Based on expected pharmacology and reduced Fc effector function, the risk for cytokine release syndrome in humans is expected to be low. There were no signs of cytokine release in the monkey studies.

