No specific data on the non-arteritic AION incidence rate are available for patients with Geographic Atrophy. Based on the limited human exposure and the epidemiological data, the Safety Monitoring Committee (SMC) and the Sponsor concluded that the findings could be coincidental, but a causal relationship to the trial drug cannot be fully excluded. Accordingly, the second SAE was reported as a SUSAR. There were a total of 12 ocular AEs; 4 were considered study drug-related and 5 were considered procedure-related. All ocular AEs, except for the optic ischaemic neuropathies were of mild intensity. All ocular AEs related to study drug or procedure recovered, with the exception of the second AION case.

Overall, 20 systemic AEs were reported. None of these were considered study drug-related and all were of mild or moderate intensity.

No Adverse Events of Special Interest (AESIs), DLEs or deaths were reported, and there was no identifiable exposure/dose-AE relationship. There were no apparent patterns of any clinically significant abnormalities in the general (ECG, vital signs, lab safety parameters) or ophthalmological (IOP, slit lamp, BCVA, SD-OCT, FAF, CFP and OCT-A) safety assessments.

For a more detailed description of BI 754132, please refer to the current IB [[c22785135](#)].

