### 7.2 PLANNED ANALYSES

#### 7.2.1 General considerations

##### 7.2.1.1 Dose escalation in the SRD part

The dose escalation will be guided by a Bayesian 2-parameter logistic regression model with overdose control [[R13-4803](#), [R13-4806](#)]. For a given dose, the EWOC criterion is that there should be less than 25% risk that the true ocular and systemic DLE rate is above 0.25. The BLRM will not be used for the analysis of the primary endpoint.

The model is given as follows:

$$\text{logit}(\pi_d) = \log(\alpha) + \beta * \log(d/d^*),$$

where  $\text{logit}(\pi) = \log(\pi/(1-\pi))$ ,  $\pi_d$  represents the probability of having a DLE in the evaluation period at dose  $d$ ,  $d^* = 6$  mg is the reference dose, allowing for the interpretation of  $\alpha$  as the odds of a DLE at dose  $d^*$ , and  $\theta = (\log(\alpha), \log(\beta))$  with  $\alpha, \beta > 0$  is the parameter vector of the model.

The estimated probability of a DLE at each dose level from the model will be summarized using the following intervals:

Target toxicity: [0.00, 0.25]

Over toxicity: [0.25, 1.00]

The BLRM-recommended dose for the next cohort is the dose level with the highest posterior probability of the DLE rate falling in the target interval [0.00, 0.25] among the doses fulfilling EWOC. Thus, it should be unlikely (< 25% posterior probability) that the DLE rate at that dose will exceed 0.25. However, the maximum allowable dose increment for the subsequent cohort will be no more than 233% from the previous dose up to doses of 3 mg, and to a maximum of 100% from the previous dose from dose 3 mg onwards. Dose escalation will continue up to the 6 mg dose as long as the EWOC criterion for the next dose level is fulfilled. At the final dose, at least 6 treated patients are required. However, the SMC may decide to include an additional number of patients at this dose level.

Since a Bayesian approach is applied, a prior distribution  $f(\theta)$  for the unknown parameter vector  $\theta$  needs to be specified. This prior distribution will be specified as a mixture of three multivariate normal distributions, i.e.

$$f(\theta) = a_1 f_1(\theta) + a_2 f_2(\theta) + a_3 f_3(\theta)$$

with  $a_i$ ,  $i = 1, 2, 3$  the prior mixture weights ( $a_1 + a_2 + a_3 = 1$ ), and  $f_i(\theta) = \text{MVN}(\mu_i, \Sigma_i)$ , the multivariate normal distribution of the  $i$ -th component with mean vector  $\mu_i$  and covariance matrix  $\Sigma_i$ , where

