2*	21	77.0	0.2	22.8	12.7 (3-21)	1.86 (1-7)
3	21	65.8	9.1	25.1	12.2 (3-21)	2.33 (0-7)
4*	21	97.8	1.4	0.8	17.9 (3-21)	1.95 (0-6)
5	21	76.7	4.7	18.6	13.8 (3-21)	2.06 (0-6)
6	21	77.4	14.1	8.5	13.8 (3-21)	2.40 (0-6)

\* Due to technical reasons, scenarios 1,2, and 4 could only be calculated with one additional dose level with assumed true DLE rate in the overdose range. As additional dose level, a dose of 15mg was chosen with the following assumed true toxicity probabilities: scenarios 1,2: 0.7, scenario 4: 0.6.

\*\* The stopped trials include early stopped trials (stopped due to too much toxicity), as well as trials that stopped because the maximum allowed patient number was reached before an MTD was found.

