#### Maximum number of patients =21

The case when the maximum number of patients is chosen as 21 allows the model to appropriately perform in most cases and for finding an MTD within the target dosing range with very high probability.

In scenario 1, which reflects the case that the true dose-toxicity is aligned with prior medians, 96.8% of the simulated trials declared a dose as MTD with true DLE rate in the targeted toxicity range. Note that 2.8% of the simulated trials stopped either because there was no MTD determined after 21 patients had been observed (0.5%) or because of too high toxicity for the planned doses (2.3%). This latter is mostly due to the cases that 1 DLE is observed out of 3 patients at the starting dose of 0.3 mg. In reality, this situation would rarely happen as the safety profile of starting dose is expected to be good.

In scenario 2, the assumed dose toxicities are higher than in scenario 1. This results in a higher percentage of early stopped trials (about 23%). In this case, about 77% of the trials would end with an estimated MTD within the targeted toxicity range, and 0.2% in the overdosing range.

In Scenario 3 (high-toxicity scenario), only 65.8 % of the trials declared a dose as MTD with true DLE rate in the targeted toxicity range. In 9.1% of the trials, the estimated MTD was in

the overdosing range. Scenario 4 (low-toxicity scenario) shows the best results, i.e. the lowest number of stopped trials and the highest number of trials with estimated MTD in the target range, as would be expected.

Scenarios 5 and 6 showed reasonable operating characteristics, given the quite large deviations of the assumed true dose-toxicity curve from the assumptions underlying the BLRM.

The mean patient numbers range from 12.2 patients (Scenario 3) to 17.9 patients (Scenario 4), and the maximum number of patients was 21. Therefore, the patient numbers are as expected and increase when moving away from the high-toxicity scenario.

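### The expected SRD size of about 17 comes from simulations that include a 15 mg level the trial does not have; on the four planned doses it is about 15, with fewer than one expected DLE

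*Protocol*

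**What the plan says.** Protocol section 7.5 gives two sizes for the SRD part. The first is a count: "If no DLE occurs, 15 DLE evaluable patients will be treated in this trial part", that is 3+3+3+6. The second is attributed to the simulations in Appendix 10.4: "about 17 evaluable patients are expected to be treated in the dose escalation part for the model to have reasonable operating characteristics". No scenario is named.

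Table 10.4:3 covers six true dose-toxicity scenarios at maximum sizes of 18 and 21. Scenarios 1, 2 and 4 are starred. The footnote explains that, for a technical reason, they could be run only with one more dose level in the overdose range: "As additional dose level, a dose of 15mg was chosen with the following assumed true toxicity probabilities", namely 0.7 in scenarios 1 and 2 and 0.6 in scenario 4.

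The planned doses are 0.3, 1, 3 and 6 mg. Section 1.2 (Toxicology) says "the maximum dose in human should not exceed 6 mg/eye". Section 7.2.1.1 limits increments "to a maximum of 100% from the previous dose from dose 3 mg onwards", whereas the simulations allowed steps of up to 234% throughout.

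The Appendix 10.4 text quotes starred results as performance of the model. For scenario 2 at a maximum of 21, "about 77% of the trials would end with an estimated MTD within the targeted toxicity range, and 0.2% in the overdosing range".

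**The concern.** The simulation-based sample size in section 7.5 appears to belong to a five-dose design. The footnote discloses the extra level, but neither section 7.5 nor the Appendix 10.4 text carries the caveat.

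The extra level affects both size and DLE count. A DLE-free trial must continue past 6 mg, and the patients treated at 15 mg face a DLE rate of 0.6 or 0.7. The starred rows therefore overstate the patients and, far more, the DLEs to expect.

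What is at stake is interpretation. Section 1.2 reports 15 SRD patients completed and states "No Adverse Events of Special Interest (AESIs), DLEs or deaths were reported". A report that cited section 7.5 or Table 10.4:3 as the expectation would set this result against the wrong benchmark.

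**Working it through.** **1. Which rows give about 17.** Mean patients in Table 10.4:3 (maximum 18 / maximum 21):

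| Scenario | Mean N | 15 mg added |
|---|---|---|
| 1 | 16.5 / 16.7 | yes |
| 2 | 12.2 / 12.7 | yes |
| 3 | 11.5 / 12.2 | no |
| 4 | 17.6 / 17.9 | yes |
| 5 | 13.1 / 13.8 | no |
| 6 | 13.3 / 13.8 | no |

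Only scenarios 1 and 4 fit. Because section 7.5 names no scenario, this link is an inference.

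**2. Could 15 mg be reached under the protocol's rules?** The step from 6 mg is (15 − 6)/6 = 150%, above the 100% limit in section 7.2.1.1 but inside the 234% used in the simulations.

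**3. Checks that need no model.**

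- *Upper bound on DLEs.* Expected DLEs are the sum over doses of true rate × expected patients, so they cannot exceed the highest rate × mean N. Scenario 1: 0.101 × 16.5 = 1.67, table 1.99. Scenario 4: 0.100 × 17.6 = 1.76, table 1.91. Both exceed what would arise if every patient received 6 mg.
- *Overdosing MTDs.* The highest planned-dose rates in scenarios 1, 2 and 4 are 0.101, 0.212 and 0.100, all below 0.25. An MTD in the overdosing range is impossible on the planned doses, yet the table gives 0.1 to 1.9%.
- *DLE-free course.* On the planned doses it takes 3+3+3+6 = 15 patients; with 15 mg added, 3+3+3+3+6 = 18.
- *Probability of no DLE on the 3/3/3/6 course.*
  - Scenario 1: 0.993³ × 0.983³ × 0.952³ × 0.899⁶ = 0.424
  - Scenario 2: 0.933³ × 0.904³ × 0.853³ × 0.788⁶ = 0.089
  - Scenario 4: 0.999³ × 0.995³ × 0.990³ × 0.900⁶ = 0.506
  - With 15 mg (3/3/3/3/6): 0.0004, 0.0001 and 0.003
- *Published DLE ranges.* At maximum 21 the ranges for scenarios 1 and 2 start at 1, so none of 1000 simulated trials was DLE-free. The planned doses would give about 424 and 89.

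**4. Reproducing the table, then removing 15 mg.** Every cohort outcome was enumerated exactly. Inputs were the section 7.2.1.1 mixture prior, the EWOC rule (posterior probability below 0.25 that the DLE rate is at least 0.25), cohorts of 3, the highest admissible dose within a 234% step, an MTD once at least 6 patients have been treated at the recommended dose, and a maximum of 18 or 21. As a check, prior overdose probabilities came out at 0.082, 0.124, 0.201 and 0.306, against 0.083, 0.124, 0.201 and 0.304 in Table 7.2.1.1:2.

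Mean N / mean DLEs:

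| Scenario, max | Table 10.4:3 | Enumerated with 15 mg | Four planned doses |
|---|---|---|---|
| 1, 18 | 16.5 / 1.99 | 16.40 / 1.98 | 14.70 / 0.73 |
| 1, 21 | 16.7 / 2.01 | 16.6 / 1.99 | 14.70 / 0.73 |
| 2, 18 | 12.2 / 1.79 | 12.02 / 1.77 | 11.53 / 1.39 |
| 2, 21 | 12.7 / 1.86 | 12.2 / 1.8 | 11.54 / 1.39 |
| 4, 18 | 17.6 / 1.91 | 17.55 / 1.94 | 15.53 / 0.62 |
| 4, 21 | 17.9 / 1.95 | 17.8 / 1.95 | 15.53 / 0.62 |

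Keeping 15 mg but applying the 100% limit returns the four-dose results exactly.

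**5. Sensitivity.** One decision is borderline: data scenario 7 of Table 10.4:1, where the protocol gives an overdose probability of 0.253 at 6 mg. The results above follow the protocol's decision. A coarser grid that puts this value at 0.248 reverses it and gives four-dose sizes of 14.4 (scenario 1) and 15.0 (scenario 4), with DLEs of 0.72 and 0.62.

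**6. Target-range MTD rate, same model with and without 15 mg.** At maximum 18 it rises from about 90 to 97.8% (scenario 1), about 74 to 78.4% (scenario 2) and about 90 to 99.7% (scenario 4). At maximum 21 the change is under 2 points: 97.4 to 97.8, 78.1 to 78.5 and 98.1 to 99.7%.

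**The case against.** The strongest reply is that nothing is hidden and no decision depends on the figure. The footnote states the extra level and its assumed rates, and section 7.5 sends the reader to that appendix. The error is conservative and the SRD part is complete. The BLRM is not used for the primary endpoint analysis, and no SAP analysis uses Table 10.4:3. This limits the consequences, but a footnote does not make the section 7.5 figure a property of the four-dose design.

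About 17 can also be read as a planning allowance, since the four-dose courses worked through in Table 10.4:1 include 15 and 18 patients. But section 7.5 presents it as an expectation from the simulations.

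The DLE ranges start at 0 in scenarios 1, 2 and 4 at maximum 18, and in scenario 4 at maximum 21. That is true, but it does not rescue the rows. With 15 mg, 1000 trials would contain about 0.4, 0.1 and 3 DLE-free trials, so a minimum of 0 or 1 is compatible with that design. The minimum is supporting evidence only; the upper bound on DLEs is firmer.

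The fair technical criticism is that the enumeration does not match every row. In scenario 3 it gives a mean N of 10.0 against 11.5 at maximum 18. In scenario 5 the target rate is 81.7% against 69.7%, and in scenario 6 about 4% stop against 11.5%. It also does not match the published target and stopped percentages of the starred rows at maximum 18. The percentages in step 6 are therefore like-for-like changes within one model, not replacement values. Nothing is claimed about scenarios 3, 5 and 6.

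**Conclusion.** The point holds. The figure of about 17 fits only rows simulated with a dose level outside the trial. On the four planned doses the expected size is 14.7 in scenario 1 and 15.5 in scenario 4, roughly two patients fewer than the table; scenario 2 gives 11.5. The DLE column is further off: 0.73, 1.39 and 0.62 in scenarios 1, 2 and 4, against about 2.0, 1.8 and 1.9.

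The observed SRD result, 15 patients without a DLE, is unremarkable under scenarios 1 and 4 on the planned doses (42% and 51%). Under the starred design a DLE-free trial would occur in at most 0.3% of cases.

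The conclusion rests on reading about 17 as scenarios 1 and 4, and on the documented prior and rules. With 15 mg included, those inputs reproduce the published mean N for scenarios 1 and 4 to about 0.1, and the mean DLEs in all three starred scenarios to within 0.1. That the starred DLE means in scenarios 1 and 4 cannot come from the planned doses follows from the protocol's own figures. Planned enrolment, doses, escalation rules and analyses are unaffected.

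**What to change.** - Re-run scenarios 1, 2 and 4 with the four planned doses and the section 7.2.1.1 increment limits. Replace the starred rows of Table 10.4:3 and the Appendix 10.4 sentences that quote them.
- Restate section 7.5 from the re-run, naming the scenario. About 15 evaluable patients is the figure to expect under scenarios 1 and 4; it does not apply to scenario 2.
- For scenarios 1, 2 and 4, recheck the statement under the maximum of 18 that most early stops come from reaching the patient limit. In the four-dose enumeration at most 0.2% of trials stop for that reason, while 2.2%, 21.5% and 0.3% stop for toxicity.
- If there is no re-run, repeat the 15 mg caveat in section 7.5 and say that it also inflates the DLE column.

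The cost is a short simulation of three scenarios and the replacement of stated figures.
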